2.0 Outcomes

2.1 Primary outcome: The primary efficacy endpoint of this double-blind, placebo-controlled phase IIa trial is a binary indicator for whether a patient would be alive and free of invasive mechanical ventilation at 28 days. The outcome will be summarized as the proportion of patients alive and free of invasive mechanical ventilation at 28 days in those receiving dupilumab in addition to standard of care (treatment arm) compared to those receiving solely standard of care management (placebo arm).

2.2 Secondary outcomes:

2.2.1 Eosinophilia as the safety outcome: The safety endpoint of this study is a binary indicator for whether a patient would have eosinophilia, which is defined as an absolute eosinophil count $> 0.6 \text{ k}/\mu\text{l}$ at ≥ 1 measurement throughout the study period. The outcome will be summarized as the proportion of patients with eosinophilia for treatment arm and placebo arm respectively. Complete blood counts with differentials

and complete metabolic panels will be measured on Day 0, 2, 5, 7, 14, 28 and 60. Day 7, 28 and 60 optional, although recommended, if patient discharged within the time frame.

2.2.2 **Other secondary safety and efficacy outcomes:**

- Cumulative incidence (defined as number of new events divided by the total number of individuals in the population at risk for the time interval) of grade 3 and 4 adverse events, serious adverse events or death including: injection site reactions, eye/eyelid inflammation, conjunctivitis, oropharyngeal pain, insomnia, tooth ache, gastritis, arthralgia, bacterial pneumonia, herpes viral infection, hypereosinophilic syndrome, hypersensitivity reaction.
- Prevalence of B.1.1.7 and B.1.351 and other SARS-CoV-2 lineages in study cohort: Day 0.
- Plasma total Immunoglobulin E (IgE) levels: Day 0 and 14.
- Plasma inflammatory markers (C-reactive protein and ferritin): Day 0, 7 and 14. Day 7 optional if patient discharged.
- Plasma cytokine levels including TARC (CCL17), YKL40, eotaxin 3 (CCL26), IL-13, IL-4, Arg1, Hyaluronan, soluble ST2: Day 0, 2, 5, 7, 14, and 28. Day 7 and 28 optional if patient discharged.
- Change in PaO₂/SaO₂ to FiO₂ ratio: Day 0, 2, 5, 7 (if patient remains inpatient throughout)
- All-cause mortality rate at 28 days.
- Hospital length of stay (LOS)
- ICU LOS
- Proportion of patients alive and free of invasive respiratory failure at 28 days.
- Proportion of patients alive and free of invasive mechanical ventilation at 60 days.
- Proportion of patients alive and free of invasive mechanical ventilation at 90 days.
- Proportion of patients alive and free of invasive mechanical ventilation at 120 days.
- Proportion of patients alive and free of invasive mechanical ventilation at 150 days.
- Proportion of patients alive and free of invasive mechanical ventilation at 180 days.
- Proportion of patients alive and free of invasive mechanical ventilation at 270 days.
- Proportion of patients alive and free of invasive mechanical ventilation at 360 days.
- National Institute of Allergy and Infectious Diseases (NIAID) 8-point ordinal scale (see Appendix): Day 0, 2, 5, 7, 14, 28, 60, 180 and 360.
- Need for vasopressors
- Need for renal replacement therapy
- Need for extracorporeal membrane oxygenation (ECMO)

3.0 General considerations

3.1 Analysis populations: Each primary and secondary efficacy outcome measure will be analyzed for the intent-to-treat (ITT) and evaluable population. The intent-to-treat principle is that participants will be analyzed in the groups to which they were randomized, regardless of whether they received the randomized study medication. Another analysis population of interest is the as-treated population. The as-treated population will consist of only participants who were inducted onto study medication, even one dose of drug. Safety outcome will be primarily analyzed for the as-treated population.

Major differences in the results for the ITT and as-treated populations, if any, will be further explored. While there is every intention to be complete in describing the analyses to be performed, it is not possible to anticipate every contingency, and some adjustments may be required to meet constraints posed by the structure of the data. Constraints such as non-linearity, non-normality, etc. may lead to different but more appropriate approaches to analysis.

3.2 Testing of Distribution assumptions: Empirical distributions of all variables will be visually inspected to detect outliers. The underlying proposed statistical methods for each analysis will be examined, primarily through inspection of graphical displays, standardized residuals, or influence diagnostics. Where appropriate and/or necessary, transformations will be utilized for continuous measures such as biomarker data, or categorized biomarkers will be analyzed.

3.3 Interim analysis: there is no formal scheduled interim analysis with respect to the primary efficacy outcome and thus the sample size estimation would not be altered. However, analysis for some selected biomarkers will be performed after the 14th day of the 20th patient enrolled. Particularly, the proportion and rate of change of C- reactive protein and ferritin levels will be calculated from day 0 and day 14 time points to determine efficacy trends between the two treatment groups. Additionally, percentage of eosinophilia will be calculated between the two groups to determine safety trend. Data will be analyzed by a third party and remain blinded to the study investigators. We expect greater changes in C-reactive protein and ferritin for patients receiving Dupilumab than those receiving placebo and no significant differences in eosinophilia between the two groups.

3.4 Software: All analyses will be performed utilizing SAS® version 9.4. All statistical tests will be conducted at the 5% Type I error rate (two-sided). When multiple tests are conducted, the chance of finding a significant difference in one of the tests, when in fact no difference exists, is greater than the stated Type I error rate. The investigators are aware of the multiple testing issues and will interpret results with caution and use confidence intervals where possible.

4.0 Analysis of demographic and baseline data:

The demographic variables for this study include age, gender, race, ethnicity, and BMI, etc. The baseline clinical characteristics include disease severity, symptoms, comorbid conditions, days

from COVID-19 symptom onset, and baseline blood lab results, etc.

Descriptive statistics for baseline and demographic variables will be presented for patients randomized to each of the treatment arms and overall. Descriptive statistics will include N, mean, standard deviation, median, 25th and 75th percentiles, minimum and maximum for continuous variables and proportions and percentages for categorical variables. In general, randomization is expected to produce balance at baseline between the two arms of the trial, formal statistical comparisons of treatment groups with respect to baseline characteristics will not be necessary. However, since this is a relatively small study, the differences in baseline characteristics between the treatment arms will be evaluated exploratorily for better understanding the study population. The updated CONSORT statement no longer recommends formal testing of statistical significance of differences between baseline characteristics.

5.0 Efficacy analyses:

5.1 General analysis strategy: The difference between dupilumab and placebo arms in outcome measures will be primarily analyzed under ITT principle, regardless of patient's use of rescue medications, protocol violations, or investigational product discontinuation. The difference will be tested initially with Chi-square for categorical measures (e.g., the primary efficacy endpoint) and two-sample t-test or Wilcoxon rank sum test for continuous measures (e.g., biomarkers). Due to the relatively small sample size in the study, the adjusted treatment effect of dupilumab will be estimated exploratively in the generalized linear regression for the primary and secondary outcomes to account for the potential impact of patient characteristics (e.g., age, sex, race and co-morbidities). Data transformation will be considered for the outcomes with skewed distribution such as hospital length of stay (LOS) and ICU LOS. The trajectory of each immune biomarker over the follow-up time points will be plotted to characterize the change of immune responses over time, and difference in biomarker (or transformed biomarker to improve normal distribution, if necessary) trajectories between the two study arms will be assessed in the mixed effects model.

Since this is intended to be an early stage, proof of concept study for which the primary goal is to inform future trials rather than to perform formal hypothesis testing, no multiplicity adjustment is planned. In addition, machine learning methods such as random forests algorithm will be applied to fully evaluate the treatment effect and predictability of dupilumab and other important predictors on the outcomes non-parametrically.

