## 1.0 SUMMARY

**Background:** Our research group has shown that high interleukin (IL)-13 is associated with respiratory failure in COVID-19 and that IL-13 inhibition protects in a mouse model of SARS-CoV-2 infection. IL-13 is a known cause of pulmonary inflammation in asthma and interstitial lung disease. We have discovered that IL-13 neutralization lessens the severity of COVID-19 and reduces hyaluronan (HA), an extracellular matrix polysaccharide previously implicated in other inflammatory pulmonary diseases, deposition in mouse lung parenchyma. It is therefore biologically plausible that IL-13 contributes to the long-haul pulmonary compromise seen in patients with severe COVID-19, potentially through promotion of HA synthesis. We hypothesize that neutralization of IL-13 will protect from acute and chronic pulmonary damage by blocking acute HA synthesis and inflammation downstream of IL-13.

**Clinical Experience:** We have conducted a phase IIa randomized double-blind placebo-controlled trial to assess the safety and efficacy of dupilumab plus standard of care versus placebo plus standard of care in mitigating respiratory failure and death in those hospitalized with COVID-19 (HSR 210184, enrollment completed/closed November 2021). Through this trial we found that dupilumab was safe for use in this population and that there was a reduced 60-day mortality in those who received dupilumab plus standard of care regimens versus placebo plus standard of care regimens. These findings implicate dupilumab as a promising and novel treatment for those hospitalized with COVID-19. Given this, along with our pre clinical data showing IL-13 influence on pulmonary injury, we plan to determine differences in post recovery pulmonary function between those who were randomized to the dupilumab arm versus placebo during acute COVID-19 infection in the HSR 210184 study cohort 1 year after enrollment.

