### **3.2 Experience with the use of dupilumab in COVID-19**

Dupilumab, an anti-interleukin-4 receptor- $\alpha$  monoclonal antibody, leading to blockage of IL-4 and IL-13 signaling, has been FDA approved for treatment of moderate to severe atopic dermatitis since 2017. It has been successfully shown to reduce disease severity in not only those with atopic dermatitis but in other allergic diseases where Th2 cytokines have been implicated, including asthma and chronic rhinosinusitis. Original clinical trials noted excellent safety profiles in addition to favorability in its use when considering the negative impacts of long term steroid use in these patients.

We have previously conducted a phase IIa randomized double-blind placebo-controlled trial to assess the safety and efficacy of dupilumab plus standard of care versus placebo plus standard of care in mitigating respiratory failure and death in those hospitalized with COVID-19. Subjects were followed prospectively for 60 days, with collection of clinical outcomes, adverse events and immunologic biomarkers at multiple time points throughout the study period. Through this trial we found that dupilumab was safe to use for this indication, that there was reduced 60-day mortality in those who received dupilumab compared to placebo and that there was a trend toward reduction in ICU admission in the dupilumab group, all of which implicated dupilumab as a promising treatment for those hospitalized with moderate to severe COVID-19.

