1.0 Introduction

1.1 Study objectives: The primary objective is to determine the efficacy of dupilumab use plus standard of care management in patients hospitalized with moderate to severe COVID-19 infection compared to placebo plus standard of care management assessed by the proportion of patients alive and free of invasive mechanical ventilation at 28 days. The secondary objectives are to: (1) evaluate the safety of Dupilumab use in terms of eosinophilia in patients hospitalized with moderate to severe COVID-19 infection, (2) compare clinical outcomes on Dupilumab versus placebo across a range of secondary clinical safety and efficacy domains, and (3) evaluate the immunologic and biologic end points of inhibition of type 2 inflammation.

1.2 Study design: This is a randomized, double-blind, placebo-controlled, superiority phase IIa trial to assess the safety and efficacy of dupilumab use in hospitalized patients with moderate to severe COVID-19 infection. A total of 40 eligible subject will be enrolled and randomized in a 1:1 ratio to receive either dupilumab or placebo, stratifying on the disease severity measured by the required oxygen $\leq 15\text{L}$ or $> 15\text{L}$ by nasal cannula. Both arms will receive standard of care management per current National Institutes of Health (NIH) COVID-19 treatment guidelines (<https://covid19treatmentguidelines.nih.gov/>) in addition to their randomized treatments. Patients will be followed prospectively for up to 60 days after enrollment.

1.3 Database Sources: Completed forms and electronic data will be entered into the data management system in the REDCap platform. Only authorized individuals shall have access to electronic CRFs.

1.4 Randomization:

In this randomized, double-blind, placebo-controlled Phase IIa trial, a total of 40 eligible subjects will be enrolled and randomized in a 1:1 ratio to receive either dupilumab or placebo, stratifying on the disease severity, which is measured by the required oxygen $\leq 15\text{L}$ or $> 15\text{L}$ by nasal cannula. Both arms will receive standard of care management per current National Institutes of Health (NIH) COVID-19 treatment guidelines (<https://covid19treatmentguidelines.nih.gov/>) in addition to their randomized treatments.

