5.3 Secondary outcomes

5.3.1 Eosinophilia as the safety outcome: Eosinophilia is a binary indicator for a patient

to have an absolute eosinophil count $> 0.6 \text{ k}/\mu\text{l}$ at ≥ 1 measurement based on the blood counts with differentials and complete metabolic panels on Day 0, 2, 5, 7, 14, 28 and 60 (Data on Day 7, 28 and 60 would be optional). The outcome will be summarized as the proportion of patients with eosinophilia and the difference in the proportions between the two study arms will be evaluated with Chi-square test. The odds ratio of having eosinophilia for Dupilumab vs. placebo and its 95% CI will also be estimated in logistic regression, with adjustment for other covariates.

5.3.2 Other secondary safety and efficacy outcomes:

- Cumulative incidence rate of adverse events (injection site reactions, eye/eyelid inflammation, conjunctivitis, oropharyngeal pain, insomnia, tooth ache, gastritis, arthralgia, bacterial pneumonia, herpes viral infection, hypereosinophilic syndrome, hypersensitivity reaction, other grade 3 or 4 adverse events, serious adverse events or death) is defined as number of adverse events divided by the total number of individuals in the population at risk for the time interval. The rate ratio of adverse events for Dupilumab vs. placebo and its 95% CI will be analyzed in Poisson regression, in which the follow-up time interval will be considered as the offset. Adjusted analysis for other covariates will be performed, as necessary. Mortality at 60 days will be analyzed as the time to event response. Survival probabilities will be estimated by the Kaplan-Meier method, and the difference in the mortality risk between the two treatment groups will be evaluated by the log-rank test and further in Cox regression, adjusting for the baseline covariates. For the analysis of mortality over the first year, additional adjustment for dynamic mechanical ventilation effect will be considered by including being on ventilation as a time-vary covariate in the Cox regression.
- Plasma total Immunoglobulin E (IgE) levels on Day 0 and 14 will be considered as continuous responses, and difference between treatment arms will be evaluated by t-test or Wilcoxon test initially, and adjusted difference and its 95% CI will be estimated from linear regression. Further, changes of IgE from Day 0 to Day 14 will also be explored and the difference between the two study arms will be analyzed similarly.

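### With about 20 patients per arm, a non-significant eosinophilia chi-square is weak evidence on the named safety endpoint, and the only planned interval for the difference may not be estimable

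*SAP*

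**What the plan says.** SAP 2.2.1 makes eosinophilia the safety endpoint: an absolute count above 0.6 k/µl at one or more measurements, compared as proportions by arm.

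- **Interim (SAP 3.3).** An "analysis for some selected biomarkers will be performed after the 14th day of the 20th patient enrolled". For safety, "percentage of eosinophilia will be calculated between the two groups to determine safety trend". The section closes with an expectation: "We expect greater changes in C-reactive protein and ferritin for patients receiving Dupilumab than those receiving placebo and no significant differences in eosinophilia". A third party does the analysis, and the investigators stay blinded. No test, threshold or action is given for eosinophilia at this look.
- **Final (SAP 5.3.1).** After the arm proportions, "the difference in the proportions between the two study arms will be evaluated with Chi-square test". An odds ratio with 95% CI from logistic regression, adjusted for other covariates, is also planned.
- **Size and level.** Forty patients are "randomized in a 1:1 ratio to receive either dupilumab or placebo" (SAP 1.2 and 1.4). SAP 3.4 sets all tests at two-sided 5%.
- **Aim (SAP 7.0).** The emphasis is exploratory estimation, including of eosinophilia. No eosinophilia rate, relevant excess or power is stated.
- **Extension protocol.** Section 1.0 says: "Through this trial we found that dupilumab was safe for use in this population". Section 3.2 says: "Through this trial we found that dupilumab was safe to use for this indication". Neither statement is qualified by trial size or by an interval.

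**The concern.** For a safety endpoint, the useful question is how large an excess the data can rule out. The SAP instead describes the expected finding as the absence of a significant difference and evaluates the endpoint with a significance test. In a trial this small, non-significance is a common result even when the drug raises eosinophilia by a sizeable amount.

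An interval would correct this, but the one planned for the arm difference is fragile. A logistic odds ratio has no finite maximum-likelihood estimate when one arm has no events, and that can easily happen with 20 patients. The reader may then have only two proportions and a p-value.

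At stake is how the eosinophilia result is carried into the safety account of the parent trial and into planning of later trials.

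**Working it through.** **The plan's own figure.** The only power figure is for the primary endpoint (SAP 7.0): 79.5% versus 97.2%, one-sided 10%, score test, 75% power. Exact enumeration of the pooled score test (z > 1.2816) with 20 per arm gives 75.1%, so it is reproduced. There is no corresponding figure for eosinophilia.

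**Inputs.** From the documents: 20 per arm at the end, and two-sided 5%. An even split of the first 20 patients is assumed, giving about 10 per arm at the interim. Placebo rates of 0%, 5% and 10% and excesses of 10 to 30 points are also assumed.

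**Step 1: what counts as significant.** The uncorrected chi-square is X² = d² / [p(1−p)(2/n)], where d is the difference in proportions and p the pooled proportion. The critical value is 3.841.

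- 5/20 v 1/20: 0.20² / (0.15 × 0.85 × 0.1) = 3.14, p = 0.08, not significant.
- 6/20 v 1/20: 0.25² / (0.175 × 0.825 × 0.1) = 4.33, significant.
- 3/20 v 0/20: 0.15² / (0.075 × 0.925 × 0.1) = 3.24, p = 0.07, not significant.
- 4/20 v 0/20: 0.20² / (0.10 × 0.90 × 0.1) = 4.44, significant.

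**Step 2: miss rates.** The two binomial distributions are enumerated exactly. A miss is any result not significant in the direction of more eosinophilia on dupilumab. For example, with placebo 0% and dupilumab 20%, a miss is 3 or fewer events in 20: probability 0.411.

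| Per arm | Excess | Placebo 0% | 5% | 10% |
|---|---|---|---|---|
| 20 | 10 points | 87% | 85% | 86% |
| 20 | 15 points | 65% | 71% | 76% |
| 20 | 20 points | 41% | 56% | 64% |
| 20 | 30 points | 11% | 28% | 38% |
| 10 | 20 points | 88% | 86% | 86% |
| 10 | 30 points | 65% | 68% | 71% |

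The rows for 10 per arm show what such a test would do at the interim; SAP 3.3 names none there. With 20 per arm, 80% power needs an excess of 26, 34 and 38 points at the three placebo rates.

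The level matters. SAP 7.0 uses one-sided 10% for its power statement, and at that level 5% versus 25% would be missed 27% of the time instead of 56%. SAP 3.4, however, puts all tests at two-sided 5%.

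**Step 3: what non-significant results leave open.** Upper limits are from the Miettinen-Nurminen two-sided 95% interval. For 0/20 v 0/20 the upper limit D solves D / √[D(1−D)/20 × 40/39] = 1.96, so D/(1−D) = 3.84 × 0.05 × 1.0256 = 0.197 and D = 0.165.

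| Dupilumab v placebo | Upper limit for the excess |
|---|---|
| 0/20 v 0/20 | 16 points |
| 3/20 v 0/20 | 36 points |
| 5/20 v 1/20 | 43 points |

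Newcombe limits for the last two rows are 36 and 42 points.

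**Step 4: chance that the odds ratio fails.** The probability of no placebo events in 20 patients is 0.95²⁰ = 36% at a 5% rate and 0.90²⁰ = 12% at 10%. At 0% it is certain. If both arms ran at 5%, the chance that at least one has none is 1 − (1 − 0.358)² = 59%. A risk difference with a score or exact interval exists in all these cases.

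**The case against.** The strongest objection is that the SAP contains no rule equating non-significance with safety. SAP 3.3 states a prediction, in the same sentence as one about C-reactive protein and ferritin. It attaches no test or decision to the interim percentages. **This stands.** A reader might infer that safety is declared from a non-significant test; the text does not say so.

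A reader might also infer that real harm would usually be read as safe. The documents do not support that. Eosinophilia here is a laboratory threshold. Adverse events, serious adverse events, hypereosinophilic syndrome and death are analysed separately, with a Poisson rate ratio and 95% CI and with survival methods (SAP 2.2.2, 5.3.2 and 6.0). Nor can the word safe in Protocol 1.0 and 3.2 be traced to the eosinophilia test; it may rest on those other data.

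It would also go too far to say that the final test misses most relevant excesses. The documents define no relevant excess. Of the six final-analysis cells for 20 and 30 points, four have miss rates below 50%.

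Finally, estimation is already planned: arm proportions, an odds ratio with 95% CI, and a general commitment in SAP 3.4 to use confidence intervals where possible. This stands in part. The SAP 3.4 commitment is written about multiple testing, which concerns false positives. The odds ratio is covariate-adjusted, can fail with zero events, and is not linked to any statement of what excess is excluded.

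**Conclusion.** The point holds for the eosinophilia endpoint only. With about 20 per arm, the two-sided 5% chi-square misses 10- and 15-point excesses more often than it finds them at every assumed placebo rate. For 20 points this holds at 5% and 10% but not at 0%, and for 30 points at none of them. A non-significant result can leave an excess of 16 to 43 points open in the examples above, so it should not be read as reassurance. The planned interval for the arm difference cannot be relied on to fill the gap.

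The miss rates rest on assumed placebo rates of 0% to 10%, the uncorrected chi-square and equal arms. The upper limits in Step 3 need no assumed event rate. No conclusion follows about clinical harms, or about whether the protocol's safety statement is right; its basis is not visible in these documents.

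**What to change.** - **SAP 5.3.1.** Make the unadjusted risk difference (dupilumab minus placebo), with a Miettinen-Nurminen or exact 95% CI, the main eosinophilia result. Keep the adjusted odds ratio as supportive. Report the largest excess not excluded, and state that a non-significant chi-square is not evidence of safety.
- **SAP 3.3.** Replace the expectation of no significant difference with counts by arm and the same interval. The parent trial has closed, so this affects only how the interim look is reported.
- **Protocol 1.0 and 3.2.** Qualify the safety statement by the trial size (N = 40) and by the eosinophilia excess that the data do not exclude.

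The cost is a few sentences and one interval from data already collected, with no added patients or procedures. The downside is a more cautious safety statement.

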### 6.2 Sample Size justification

Under the protocol HSR 210184, we conducted a randomized double-blind placebo-controlled trial assessing the safety and efficacy of dupilumab for treating hospitalized patients with acute moderate to severe COVID-19, which was designed as an early stage (Phase IIa) and proof of concept study. A total of 40 patients were enrolled from June 23, 2021 through November 180 11, 2021 in the Phase IIa study, and 7 of them died by Day 60. The sample size of 40 in the original Phase II study were determined largely based on the feasibility with a primary goal to collection reliable data and obtain sufficient evidence for future trials. The current proposed study is an extension of the original Phase IIa study under the HSR 210184, to assess the post recovery of remaining 33 patients from COVID-19 with respect to pulmonary function testing (PFT), pulmonary imaging, immune biomarkers and symptoms at one-year follow-up. All data will be collected at a single visit, 1 year (i.e.,  $365 \pm 90$  days) after initial enrollment in the remaining 33 parents from the study HSR 210184. Formal sample size estimation and power analysis is not performed due to the pilot nature of this proposed follow-up study.

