5.2 Primary efficacy outcome

The primary efficacy endpoint of this study is a binary indicator for whether a patient would be alive and free of invasive mechanical ventilation at 28 days. The outcome will be summarized as the proportion of patients alive and free of invasive mechanical ventilation at 28 days and the difference in the proportions between the two study arms will be evaluated with Chi-square test. The odds ratio of being alive and free of invasive mechanical ventilation at 28 days for Dupilumab vs. placebo and its 95% confidence interval (CI) will be estimated in logistic regression, adjusting for potential baseline characteristics if necessary.

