This trial is intended to be an early stage and proof of concept study with the primary goal to collect reliable data and obtain sufficient evidence for future trials. Thus, the emphasis of the study is an exploratory estimation of effect size and incidence of adverse events in terms of eosinophilia; it is not considered as a pivotal trial for efficacy at this time. Therefore, a larger significance level (one-sided alpha=0.1), and the sample size is pre-selected based on the feasibility. Given the current decline trend in the incidence of COVID-19 positive cases, we anticipate to enroll 40 patients realistically into this randomized clinical trial, which shall be sufficient for us to collect reliable and interpretable data for proof of concept to inform future trials. The COVID-19 hospitalization data from our University of Virginia Health System between March 2020 and April 6, 2021 showed that 79.5% of COVID-19 inpatients were alive and free of mechanical ventilation at 28 days under the usual care. With 40 patients that are deemed to be feasible, we would expect Dupilumab to improve a margin of 17.7% in the proportion of patients alive and free of mechanical ventilation at 28 days. That is, it is anticipated that 97.2% of patients being alive and free of ventilation at 28 days in the Dupilumab arm. The power analysis is conducted using the one-sided Score test (Farrington & Manning) with 75% power and 10% type I error.

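### The SAP sets two unreconciled significance levels for the day-28 primary endpoint: two-sided 5% in 3.4 and one-sided 10% in 7.0. The stated 75% power is about 42% (uncorrected chi-square) at two-sided 5%.

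*SAP*

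**What the plan says.** Three sections of the SAP bear on how the primary endpoint, survival without invasive ventilation at day 28, is tested.

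- **SAP 3.4 (Software)** sets a general rule: "All statistical tests will be conducted at the 5% Type I error rate (two-sided"). It makes no exception for the primary endpoint.
- **SAP 5.2 (Primary efficacy outcome)** says "the difference in the proportions between the two study arms will be evaluated with Chi-square test" and, for the odds ratio, "its 95% confidence interval (CI) will be estimated in logistic regression". It gives neither a level nor a side for the test, but a 95% interval corresponds to two-sided 5%.
- **SAP 7.0 (Sample size estimation and power analysis)** adopts "a larger significance level (one-sided alpha=0.1), and the sample size is pre-selected based on the feasibility", and then states "The power analysis is conducted using the one-sided Score test (Farrington & Manning) with 75% power and 10% type I error". The rates assumed are 79.5% under usual care and 97.2% on dupilumab, with 40 patients in total.

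The protocol supplied with this SAP covers the one-year follow-up of the same patients. It already reports parent-trial results: in 3.2 that "there was reduced 60-day mortality in those who received dupilumab compared to placebo", and in 6.2, of the 40 enrolled, that "7 of them died by Day 60".

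**The concern.** A trial needs one rule for calling its primary result positive, and its stated power should belong to that rule. Here the general rule and the design section use different levels and different sidedness for the same endpoint. The SAP does not say that the 10% level served only for planning, nor does it exempt the primary test from 3.4.

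Two things follow. A borderline result can be called positive by citing 7.0 or negative by citing 3.4. And a reader who takes 3.4 as the rule will credit the test with 75% power that it does not have. Because some parent-trial results are already known, a threshold chosen now could look as though it was chosen with outcomes in view.

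**Working it through.** **Inputs.** Usual-care rate 0.795, dupilumab rate 0.972, difference 0.177 (all SAP 7.0). Total of 40 randomized 1:1 (SAP 1.2), taken as 20 per arm. The test is the chi-square of 5.2. The levels are one-sided 0.10 (7.0) and two-sided 0.05 (3.4).

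**The two named tests share one statistic.** The Farrington-Manning score statistic with a null difference of zero is

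z = (p_D − p_P) / √[p̄(1 − p̄)(1/20 + 1/20)], where p̄ is the pooled proportion.

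Its square is the uncorrected Pearson chi-square. So naming a score test in 7.0 and a chi-square in 5.2 is not a second mismatch. Only the cut-off differs: z ≥ 1.2816 under 7.0 and |z| ≥ 1.9600 under 3.4.

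**Exact power.** Sum Binomial(20, 0.972) × Binomial(20, 0.795) over all 21 × 21 outcomes that meet the cut-off:

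| Criterion, 20 per arm | Power | Type I error at 79.5% in both arms |
|---|---|---|
| z ≥ 1.2816 (one-sided 10%) | 75.1% | 9.9% |
| \|z\| ≥ 1.9600 (two-sided 5%) | 41.9% | 5.0% |

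The first row reproduces the SAP's 75%. The share of trials with z ≥ 1.2816 but |z| < 1.96 is 75.1% − 41.9% = 33.2%.

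**Normal approximation as a cross-check.** p̄ = (0.795 + 0.972)/2 = 0.8835. The null standard error is √(2 × 0.8835 × 0.1165/20) = 0.1015. The alternative standard error is √[(0.795 × 0.205 + 0.972 × 0.028)/20] = 0.0975. Power at two-sided 5% is Φ[(0.177 − 1.96 × 0.1015)/0.0975] = Φ(−0.22) = 41.1%. At one-sided 10% the same formula gives 68.5%, below the exact 75.1%. The SAP's figure is therefore matched by the exact calculation and not by this approximation.

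**How far the 42% can move.**

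- *Continuity correction or Fisher's test.* Expected failures under the target are 20 × 0.028 = 0.56 on dupilumab and 20 × 0.205 = 4.1 on placebo, so the variant matters. At two-sided 5%, exact power is 15.3% with a continuity correction and 25.5% with Fisher's test. SAP 5.2 does not specify a correction and does not name Fisher's test.
- *Unequal arms.* Blocks of 4 in two strata can leave each stratum up to 2 out of balance, so splits from 18:22 to 22:18 are possible. For dupilumab:placebo splits of 18:22, 19:21, 21:19 and 22:18, power is 33.6%, 42.2%, 37.9% and 50.8% at two-sided 5%, and 73.5%, 78.2%, 73.4% and 69.7% at one-sided 10%.
- *Largest possible effect.* With 100% success on dupilumab against 79.5%, power at two-sided 5% is 61.0%. No effect size reaches 75% with 20 per arm at the planned control rate.

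**A result on which the sections disagree.** Take 20/20 on dupilumab and 17/20 on placebo. p̄ = 37/40 = 0.925, and z = 0.15/√(0.925 × 0.075 × 0.1) = 0.15/0.0833 = 1.80. One-sided p = 0.036, positive under 7.0. Two-sided p = 0.072, negative under 3.4.

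**The case against.** The best reply is that the sections do different jobs. SAP 3.4 covers every test without exception, and the 95% interval in 5.2 agrees with it. The 10% level appears only in the section on sample size, where the last sentence ties it to the power calculation. On that reading 3.4 and 5.2 govern the analysis, and 7.0 records a relaxed planning level. SAP 5.1 adds that the aim is to inform later trials and not to test hypotheses formally, and 7.0 says the sample size rests on feasibility. The estimate and 95% interval would be reported identically under either level. The trial has closed to enrolment, and the one-year protocol claims no power at all.

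Much of this stands, and it limits the weight of the point. The planning-level reading is the natural one, and the fix adopts it. But the SAP does not say so, and even on that reading the 75% does not describe the test at the level set in 3.4. The exploratory aim does not remove the issue either, since the plan still names a test, sets an error rate and states a power.

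One caution also stands. The documents report 60-day mortality but not the day-28 result, nor when or at what level it was analysed. They do not show that the threshold was chosen after the fact. They show only that outcome information exists, which is a reason to date any clarification.

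**Conclusion.** The inconsistency is real and should be fixed. The SAP's 75% is correct for one-sided 10%, but at the level 3.4 sets for all tests the same design has about 42% power. That figure assumes 20 per arm, the SAP's own rates and a chi-square without continuity correction. With either of the two more conservative test variants it falls to between 15% and 26%. With plausible unequal splits of the uncorrected test it runs from 34% to 51%. Every one of these figures is well below 75%. If the target effect holds, about one trial in three would get opposite verdicts from the two sections. The consequence is confined to the reading of the primary result and of the stated power; the data, the estimate and the sample size are unaffected.

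**What to change.** Keep two-sided 5% with the 95% confidence interval as the one criterion for the primary endpoint, as 3.4 and 5.2 already imply, and say so in both. In 5.2, state that the chi-square is used without continuity correction. In 7.0, state that power at that level is about 42% for the uncorrected chi-square, and that 75% applies only at one-sided 10%.

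Because parent-trial results are already known, record this as a disclosed, dated clarification. Do not introduce a one-sided 10% primary test now.

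The cost is a change of wording and a less favourable power figure; 75% could no longer be cited for the test at the level in 3.4. No new patients, data or analyses are needed.
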